2.4. Study Procedures

Sponsor:	ObsEva							
Protocol:	18-OBE2109-00	18-OBE2109-003						
Document Version No.:	V5.0	Document Date:	13-JUN-2022					

The schedule of assessments, as outlined in the study protocol, is provided in Table 1 and Table 2.

Table 1 Schedule of Assessments – Screening and Treatment Periods

Timing ¹	Screening Period			-	Freatment	Period		
	Screening Period (up to 3 months ²)	Day 1	M1	M2	M3	M4	M5	M6
Informed Consent	x							
Inclusion-Exclusion criteria	x	x						
Demography, height, weight, medical history	x	X						

³ Only weight will be recorded.

CRS-BS-TP-000005 V 1.0

Page **19** of **127**

¹ All post-baseline visits should take place at the end of the defined period (i.e., M1 visit should be scheduled at the end of Month 1, M2 visit should be scheduled at the end of Month 2, etc.). Post-baseline visits dates are calculated from Day 1 visit date. A month is defined as 28 days/4 weeks. Visits should be scheduled ± 3 days from the calculated date.

² If required for washout of oral contraceptives, other sex hormones, or GnRH antagonists/agonists (provided that the reason for discontinuing the previous GnRH-antagonist is not lack of efficacy), a period of up to 3 months is allowed between signing the informed consent and the screening visit.

 Sponsor:
 ObsEva

 Protocol:
 18-OBE2109-003

 Document Version No.:
 V5.0

 Document Date:
 13-JUN-2022

Schedule of study assessments – Screening and Trea	atment Periods								
	Screening Period		Treatment Period						
Timing ¹	(up to 3 months ²)	Day 1	M1	M2	M3	M4	M5	M6	
mB&B	x								
Columbia-Suicide Severity Rating Scale	x	X	X	X	X	X	x	X	
ECG	X	x ⁴	x	x	x	x	x	x	
Physical examination	X				X			x	
Vital signs	x	x	X	X	X	X	x	x	
Urine pregnancy test	x	X	X	X	X	X	x	x	
TVUS of uterus	X				X			x	
Gynecological examination	X				X			X	

⁴ ECG on Day 1 should be performed twice: once before treatment and once after treatment (just before PK sampling).

CRS-BS-TP-000005 V 1.0

Page **20** of **127**

Sponsor:	ObsEva		
Protocol:	18-OBE2109-00	3	
Document Version No.:	V5.0	Document Date:	13-JUN-2022

Timing ¹	Screening Period			Т	reatment Pe	riod		
	(up to 3 months ²)	Day 1	M1	M2	M3	M4	M5	M6
Endometrial biopsy	x							x ⁵
Pap test	x							
Breast examination (mammogram if required)	x							x
Clinical laboratory & urinary protein dipstick	x	x ⁶	X	х	x ⁶	х	х	x ⁶
Blood sample for PK ⁷		x	X	X	X	x	x	X
BMD by DXA	x							X
Adverse events	x	x	X	X	X	x	X	X

⁵ If endometrium thickness in TVUS is \leq 5 mm, no endometrial biopsy will be necessary.

Page **21** of **127**

⁶ Overnight fasting is required.

⁷ PK samples should be taken after the ECG and before the daily dose of IMP, except on Day 1 when the PK sample should be taken at least 1.5 h after the IMP administration.

Sponsor:	ObsEva		
Protocol:	18-OBE2109-00	3	
Document Version No.:	V5.0	Document Date:	13-JUN-2022

Schedule of study assessments – Screening and Trea	atment Periods								
Timing ¹	Screening Period	Sereening Period Treatment Period							
	(up to 3 months ²)	Day 1	M1	M2	M3	M4	M5	M6	
Previous/concomitant medication	x	X	X	X	X	X	X	X	
Contraceptive dispensing and counselling	x	X	X	X	X	X	X	x	
Permitted analgesic prescribing/dispensing	x	x	x	x	x	x	x	x	
Vitamin D and calcium dispensing		x	x	x	x	x	x	x	
Subject eDiary completion training/check	x	X	X	X	X	X	X	x	
IMP accountability			x	X	x	X	x	x	
Dispense study drug		X	x	X	x	x	x		
Dispense ABT		x			x				

 Sponsor:
 ObsEva

 Protocol:
 18-OBE2109-003

 Document Version No.:
 V5.0

 Document Date:
 13-JUN-2022

Schedule of study assessments – Screening and Tro	eatment Periods	1						
	Screening Period	Treatment Period						
Timing ¹	(up to 3 months ²)	Day 1	M1	M2	M3	M4	M5	M6
EHP-30, EQ-5D-5L and PROMIS ⁸		X	X		X			X
mPGIS, PGIC, HRUQ and HRPQ		x ⁹	X	X	X	X	x	X
Specific monthly severity questions ⁸		x			x			x
SSIQ and PSIQ ⁸		x						x
АМН		x						
E2, LH, P4		X	X	X	X	x	x	X
SHBG		X			X			x

⁸ ClinROs (Monthly dyspareunia question, PSIQ and HRUQ) will be administered to the subject by the site staff and the responses will be filled in the eDiary. ePROs (EHP-30, EQ-5D-5L, PROMIS, PGIS, PGIC, HRPQ and SSIQ, and specific monthly severity questions) will be filled in by the subject in the eDiary.

⁹ PGIC not done at Day 1.

Sponsor:	ObsEva			
Protocol:	18-OBE2109-003			
Document Version No.:	V5.0	Document Date:	13-JUN-2022	

Schedule of study assessments – Screening and Treatment Periods								
	Screening Period (up to 3 months ²)	Treatment Period						
Timing ¹		Day 1	M1	M2	М3	M4	M5	M6
Bone biomarkers		x			x			x
Question regarding treatment received								x

Sponsor:	ObsEva			
Protocol:	18-OBE2109-003			
Document Version No.:	V5.0	Document Date:	13-JUN-2022	

Table 2 Schedule of study assessments - Follow-up Period

Schedule of study assessments – Follow-up Period						
M1 FU	M2 FU	M3 FU	M4 FU	M5 FU	M6 FU	
x	x	x	х	х	x	
X	X	x	x	х	x	
X	x	x	x	x	x	
X		x			x	
					х	
					x	
					Λ	
	M1 FU x x	M1 FU M2 FU x x x x x x x x x x x x x x x x x x	M1 FU M2 FU M3 FU X X X X X X X X X X X X X X X X X X X X X X X X X X X X X X X X X X X X X X X X X X X X X	M1 FUM2 FUM3 FUM4 FUxxx M1 FUM2 FUM3 FUM4 FUM5 FUxx	M1 FUM2 FUM3 FUM4 FUM5 FUxx	

¹ All follow-up study visits should take place at the end of the defined period (i.e. M1 FU visit should be scheduled at the end of the first month of follow-up, M2 FU visit should be scheduled at the end of the second follow-up visit, etc.). A month is defined as 28 days/4 weeks. Visits should be scheduled ± 7 days from the calculated date.

Sponsor:	ObsEva					
Protocol:	18-OBE2109-00	18-OBE2109-003				
Document Version No.:	V5.0	Document Date:	13-JUN-2022			

Schedule of study assessments – Follow-up Period							
Timing ¹	M1 FU	M2 FU	M3 FU	M4 FU	M5 FU	M6 FU	
Gynecological examination			x				
Breast manual examination			x				
Endometrium TVUS			x			x	
Endometrial biopsy	x ²	x ²	x ²	x ²	x ²	x ³	
Clinical laboratory & urinary protein dipstick	X		x ⁴				
Subject eDiary completion check	x	x	x	x	x	x	
Subject eDiary collection and deactivation						x	

Page **26** of **127**

² Endometrial biopsy will be taken only if diagnosis at preceding month was different than "benign endometrium" or if no endometrial biopsy was done at Month 6 nor at any visit since Month 6.

 $^{^{3}}$ An end-of-study biopsy is mandatory if no endometrial biopsy was obtained at M6 nor at any of the subsequent monthly visits.

⁴ Overnight fasting is required.

Sponsor:	ObsEva				
Protocol:	18-OBE21	18-OBE2109-003			
Document Version No.:	V5.0	Document Date:	13-JUN-2022		

Schedule of study assessments – Follow-up Period							
Timing ¹	M1 FU	M2 FU	M3 FU	M4 FU	M5 FU	M6 FU	
EHP-30, HRUQ, HRPQ, EQ-5D-5L and PROMIS			x			x	
mPGIS and PPGIC	X	x	x	х	x	x	
BMD by DXA						x ⁵	
E2, LH, P4	x		x				
FSH at local laboratory for subjects that do not resume menses at M3 FU visit			x				
Bone biomarkers			x				
Permitted analgesic prescribing/dispensing	X	X	X	X	X		
Vitamin D and calcium dispensing	X	x	x	x	x		

 $^{^{5}}$ Subjects with a BMD decrease from baseline of > 1.5% for lumbar spine and/or > 2.5% for total hip at Month 6 FU visit will have an additional DXA scan 6 months later.

Sponsor:	ObsEva			
Protocol:	18-OBE2109-003			
Document Version No.:	V5.0	Document Date:	13-JUN-2022	

Schedule of study assessments – Follow-up Period							
Timing ¹	M1 FU	M2 FU	M3 FU	M4 FU	M5 FU	M6 FU	
Urine pregnancy test and contraceptive dispensing and counselling	х	х	х			х	

Sponsor:	ObsEva			
Protocol:	18-OBE2109-003			
Document Version No.:	V5.0	Document Date:	13-JUN-2022	

2.5. Efficacy, Pharmacokinetic, and Safety Variables

2.5.1. Efficacy Variables

2.5.1.1. Primary efficacy endpoint

The two co-primary, composite, efficacy endpoints are clinically meaningful reduction from baseline to the last 28 days preceding the Month 3 visit (the 4-week period preceding Month 3 visit) or, for subjects who discontinue randomized treatment prior to the Month 3 visit, to the last 28 days of randomized treatment, along with a stable or decreased use of analgesics for EAP, in the mean daily assessment of 1) DYS and of 2) NMPP measured on a Verbal Rating Scale (VRS) using an electronic diary (eDiary).

Additional details on the primary endpoint definition and primary analysis are provided in Section 4.6.

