10.6.2 Prohibited Medicines

Medication listed in exclusion criteria (see section 9.2.2) will be prohibited up to Month 6.

To consider a subject who is currently taking any prohibited therapies for potential inclusion in this study, the Investigator must ensure that the subject has sufficient washout time prior to screening (see Section 10.2.1).

Strong CYP3A4 inhibitors or inducers are prohibited up to end of treatment in view of the ABT (Appendix P).

Linzagolix is considered to be a weak inhibitor of CYP2C8. Substrates to CYP2C8 with a narrow therapeutic index should be administered with caution.

Hormonal contraception including hormonal IUD must be stopped following ICF signature until 3 months after end of treatment.

When a prohibited medication or treatment is necessary for the subject's well-being, the sponsor must be notified and possible alternatives are to be discussed before administration of the prohibited medication or treatment whenever possible.

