10.7.2.1 Discontinuation criteria

During the course of the study, the subject may be discontinued for the following reasons:

- **Adverse Event:** Includes clinically significant new or worsening existing condition as judged by the Investigator. Document in the AE form.
- **Subject's Request:** Consent withdrawal, subject moved, schedule conflicts, etc. Specify the reason in the comment section of the eCRF Exit Form.
- **Protocol Violation:** Major protocol violation which may affect the subject's safety. Specify the protocol violation in the comment section of the eCRF Exit Form.
- **Lost to Follow-up:** Document with at least two phone calls and a certified letter requesting return receipt without response. Document in the comment section of the eCRF Exit Form.
- **Pregnancy:** Subjects that have been exposed to study treatment and who become pregnant during the Treatment Period will be immediately withdrawn from treatment. Pregnancies that have been exposed to study treatment and occurred up to Month 3 FU visit, or started up to 4 weeks after treatment discontinuation in case of early withdrawal will be followed up for pregnancy and neonatal outcomes at birth. Any pregnancy must be reported with the Pregnancy Surveillance Form (see section 12.6).
- **Other:** Specify in the Comments section in the eCRF Exit Form. This reason should only be used if the reason for discontinuation is not better accounted for by another category.

Discontinuation Rules at Day 1: Subjects presenting with ALT, AST, GGT or total bilirubin ≥ 2 ULN should be discussed with the Sponsor and may have to discontinue study treatment if these results are indicative of liver involvement.

Subjects presenting with a clinically significant finding in the biopsy sample collected at screening and who have completed Day 1, will have to discontinue study treatment.

Subjects who have a serum calcium level at Day 1 above 2.9 mmol/L and who have completed Day 1, should have calcium supplements interrupted. If serum calcium level at Day 1 is above 3.1 mmol/L calcium supplements **and study treatment** are to be interrupted. A repeat test of this parameter within 2 weeks under fasting conditions is to be performed. If the results of the repeat remain above 2.9 mmol/L, study treatment should definitively be discontinued and the subject should be advised to consult an endocrinologist for further evaluation.

Discontinuation Rules during the Treatment Period:

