A protocol deviation is any noncompliance with the clinical trial protocol or International Conference on Harmonization Good Clinical Practice (ICH GCP) requirements. It is the responsibility of the site investigator to use continuous vigilance to identify and report deviations. All deviations must be addressed in study source documents and reported to the reviewing IRB/IEC per their policies. The site investigator is responsible for knowing and adhering to the reviewing IRB/IEC requirements.

Sponsor:	ObsEva		
Protocol:	18-OBE2109-003		
Document Version No.:	V5.0	Document Date:	13-JUN-2022

All Protocol Deviations will be reported to the Sponsor and documented in the monitoring report. These will be classified as minor or major based on their effect on the right, safety or well-being of the subjects and/or the quality and integrity of the data, and the final rating of all deviations will be confirmed prior to database lock. The final protocol deviation file (formatted as a Microsoft Excel file) will be provided to Cytel.

Major protocol deviations will be summarized by category (if available) and by treatment group for the FAS population.

Major deviations that could potentially affect the efficacy assessments up to Month 6 and thus may exclude subjects from the PP Set may include:

- Non-compliance with inclusion criteria 3; 6; 8
- Non-compliance with exclusion criteria 2 to 10 inclusive; 12; 13; 17; 19; 20; 21; 23; 24; 25
- Non-compliance with study treatment: threshold to be defined during blinded data review meeting (e.g. IMP compliance in tablets <60% for Day1-Month 6)
- IP Dispensing error;
- Unauthorised prior or concomitant therapy;
- M3 and/or M6 Visits performed outside the +/-14 days of the theoretical visit date;
- Randomisation code broken;

All protocol deviations will be presented in the data listings.

Sponsor:	ObsEva		
Protocol:	18-OBE2109-003		
Document Version No.:	V5.0	Document Date:	13-JUN-2022

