4. STATISTICAL METHODS

4.1. Sample Size Justification

The planned sample size for this study is 150 subjects per treatment group (450 subjects in total).

An overall two-sided type I error of 0.05 will be used. As there are two linzagolix versus placebo comparisons, Bonferroni corrected p-values will be produced (raw p-values will be multiplied by two prior to comparing to 0.05). The planned sample size considers the hierarchical, fixed sequence testing of the ranked secondary endpoints as well as the co-primary endpoints. The assumptions used for the sample size calculations are based on analyses of clinically meaningful reduction in pain with a stable or decreased use of analgesics from the Phase 2b Edelweiss study. Calculations were performed using East[®] 6.5 software.

One hundred and fifty (150) subjects per treatment group will provide a power greater than 95% to reject the null hypothesis for both co-primary endpoints for either treatment group, assuming a placebo response rate of 14.6% and an active treatment response rate of 48.6% (75 mg, Edelweiss Phase II study results) or 64.7% (200 mg, Edelweiss Phase II study result) for DYS, and a placebo response rate of 18.8% and an active treatment response rate of 42.1% (75 mg, Edelweiss Phase II study result; the response rate for 200 mg in Edelweiss was lower but was inconsistent with the other doses and other timepoints for the same dose and so was not used) for NMPP. In addition, 150 subjects per treatment group provides 85% power to reject the null hypotheses for all the ranked secondary endpoints based on the observed results from the placebo and 200 mg treatment group in the Edelweiss study.

The values used for the sample size calculations assume that these responses rates are what would be seen on average when under treatment including taking into account any subjects who might withdraw from treatment early; therefore the calculations do not need to be further adjusted for dropouts.

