Intercurrent events: Increased use of EAP analgesia is a non-response in the endpoint definition. Treatment discontinuations are assessed up to the time of discontinuation. Randomized treatment will be considered, regardless of lack of compliance to treatment or treatment assignment errors. The clinical question of interest is based on a while-on-treatment strategy for discontinuation and composite strategy for analgesic use. Lack of compliance to treatment and treatment assignment errors are handled using a treatment policy strategy.

The "while-on-treatment strategy" was chosen for the intercurrent event of discontinuation of treatment for the co-primary endpoints based on the recommended strategies for addressing intercurrent events in the (then draft) ICH E9 (R1) guideline.

Sponsor:	ObsEva	ObsEva		
Protocol:	18-OBE2109-00	18-OBE2109-003		
Document Version No.:	V5.0 Document Date: 13-JUN-2022			

The response to treatment prior to the occurrence of the patient discontinuing treatment is of clinical interest for a symptomatic treatment of endometriosis-associated pain. Patients and prescribers are generally interested in what happens when a patient actually takes (and can take) the treatment. This corresponds most directly to the "while on treatment" strategy for treatment discontinuation. Of note, a comparison of patient disposition and discontinuation rates will also constitute an important aspect when interpreting the study results. In addition, a "while-on-treatment" strategy for efficacy aligns with the analysis of adverse events, which are also considered while on treatment. Moreover, as endometriosis-related pelvic pain is measured repeatedly each day, the variable can be readily calculated for the 28-day period up to the point of discontinuation and the value up to the time of discontinuation can be considered to account for the intercurrent event.

For each of the co-primary endpoints, the criterion for defining a subject as a responder over the last 28 days of randomized treatment up to the Month 3 visit will include a reduction of X or greater from baseline in pain, where X was determined by a meaningful change threshold estimation using appropriate anchors as described in Section 4.6.1, as well as stable or decreased use of analgesics for EAP. Results of the meaningful change threshold estimation 4.6.1.3.

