Mean pelvic pain scores for DYS and for NMPP will be calculated by averaging over the corresponding 28 calendar days immediately prior to and including the day of the Month 3 visit. DYS will use days with uterine bleeding, defined as those days on which the subject records any uterine bleeding or spotting in the subject eDiary; NMPP will use days with no uterine bleeding. If a subject's mean score for DYS is undefined numerically because her daily eDiary reports indicate that she did not experience uterine bleeding on any days during the 28 calendar day period, then the mean score for DYS will be set equal to zero (which reflects the absence of any DYS during that reporting time period). Similarly, if a subject's diary reports indicate that she only experienced days with uterine bleeding during the period, then the mean score for NMPP will be set equal to zero. For subjects who discontinue treatment prior to Month 3, the last available observations prior to discontinuation will be used, in order to estimate the treatment effect while under treatment, that is the 28 calendar days immediately prior to and including the last dose date. The baseline mean overall pelvic pain scores for DYS and NMPP will be calculated by averaging over the two baseline menstrual cycles (as defined in section 4.2.10), which may not be exactly 28 days each. For both DYS and NMPP, responses of "None," "Mild," "Moderate," and "Severe" will be assigned a score of 0, 1, 2, and 3, respectively.

For the assessment of stable or decreased use of analgesics for EAP (assessed separately for DYS and NMPP), the analgesic use for any defined period will be based on the mean of the total pill count for each class of rescue analgesics (endometriosis-associated). The total pill count for each class of rescue analgesic is the sum of the pill count of the corresponding class of rescue analgesic, as reported in the eDiary during the time period of interest. Baseline analgesic use will be calculated as the mean of the daily pill count of analgesics over the two baseline menstrual cycles (as defined in section 4.5.2). For the purposes of determining a stable or decreased use of analgesics, the averaging will be done over the same calendar days as used for the pelvic pain scores (i.e. for DYS days with uterine bleeding, defined as

Sponsor:	ObsEva		
Protocol:	18-OBE2109-003		
Document Version No.:	V5.0	Document Date:	13-JUN-2022

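### A prohibited hormone that stops bleeding can make a woman a dysmenorrhea responder in the primary analysis, because the SAP has no intercurrent-event rule for it

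*SAP*

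**What the plan says.** **Window.** SAP 2.5.1.1 assesses the co-primaries over the 28 days before the Month 3 visit or, "for subjects who discontinue randomized treatment prior to the Month 3 visit, to the last 28 days of randomized treatment".

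**Zero rule.** Under SAP 4.6.2.1.1, DYS is the mean pain score on days with bleeding or spotting. If the diary shows none in the window, "then the mean score for DYS will be set equal to zero (which reflects the absence of any DYS during that reporting time period". No cause of the missing bleeding is excepted. Protocol 13.5.2 has the same rule.

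**Response.** SAP 4.6.1.3 requires a DYS reduction of at least 1.10. Analgesic use, judged on the same days as the pain score, must also not have increased (SAP 4.6.2.1.1 and Appendix A).

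**Intercurrent events.** SAP 4.6.2.1.1 handles analgesics by a composite strategy: "Increased use of EAP analgesia is a non-response in the endpoint definition". Discontinuation is handled while on treatment; non-compliance and assignment errors by treatment policy. Prohibited therapy and pregnancy are not named.

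**Prohibited therapy.** Protocol 10.6.2 bars the drugs of exclusion criterion 7 up to Month 6. If one is judged necessary, the sponsor must be told and "possible alternatives are to be discussed before administration of the prohibited medication or treatment whenever possible". The section does not say whether study drug stops or continues. SAP 3.2 lists "Unauthorised prior or concomitant therapy" among deviations that may exclude a woman from the Per Protocol (PP) Set. The primary analysis uses the FAS (SAP 4.6.2.1.2).

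**Pregnancy.** Protocol 10.7.2.1: "Subjects that have been exposed to study treatment and who become pregnant during the Treatment Period will be immediately withdrawn from treatment".

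**The concern.** Two women need something beyond study drug to control their disease. One raises her analgesic use past the Appendix A tolerance of 15% and, in general, fails. The other starts a hormone that suppresses endometriosis, stops bleeding, is given a DYS score of zero and can succeed. The SAP treats the first as evidence against study drug and has no rule for the second.

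The SAP justifies its while-on-treatment strategy by interest in what happens when a patient takes, and can take, the assigned treatment. Absence of bleeding caused by another hormone does not answer that question. At stake is what the co-primary estimate means. Month 6 DYS is derived in the same way (SAP 4.6.3.1) and stands first among the ranked secondary endpoints; there such a woman would be credited with her whole baseline score as improvement.

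**Working it through.** **1. The plan's own figure.** SAP 4.1 gives 150 women per arm and states: "An overall two-sided type I error of 0.05 will be used". Since "raw p-values will be multiplied by two prior to comparing to 0.05", each comparison is tested at 0.025 two-sided. Assumed rates for 75 mg against placebo are 48.6% v 14.6% (DYS) and 42.1% v 18.8% (NMPP).

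Power = Φ{[|p1 − p2|√n − z√(2p̄(1 − p̄))] / √(p1(1 − p1) + p2(1 − p2))}, with z = 2.241.

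- NMPP: p̄ = 0.3045; (0.233 × 12.247 − 2.241 × 0.651) / 0.630 = 2.22, so 98.7%.
- DYS: p̄ = 0.316; (0.340 × 12.247 − 2.241 × 0.657) / 0.612 = 4.40, so above 99.99%.
- Both: 98.7%, as a product or as the lower bound p1 + p2 − 1. The stated power above 95% is reproduced.

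**2. A hormone user who stays on study drug.** Month 3 is Day 85, so the window is Day 58 (85 − 27) to Day 85. She is scored a DYS responder if all of these hold:

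- no bleeding or spotting after Day 57, which makes DYS zero;
- baseline DYS of at least 1.10, since baseline − 0 must reach 1.10;
- at least 28 days of treatment and at least 12 completed diary days (SAP 4.6.2.1.2);
- no increase in analgesics. For DYS this is averaged over bleeding days. With none, the average is undefined and the SAP does not say how to judge it. This gap affects every bleed-free woman, whatever the cause.

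**3. Which analyses would catch her.**

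| Analysis | Hormone user still on study drug | Pregnancy withdrawal |
|---|---|---|
| Primary, FAS | not caught | not caught if the window is bleed-free |
| SAP 4.6.5.1, stopping before Month 3 = non-response | not caught | caught, unless first detected at the Month 3 visit |
| SAP 4.6.2.2, other analgesics added | not caught (analgesic codes only) | not caught |
| PP Set | may be excluded (3.2) | excluded (six completed months required, 3.1) |

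**4. Size.** One woman is 1/150 = 0.67 points. The documents give no frequency by arm, so k women wrongly scored as DYS responders is an assumed range.

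- All on placebo: OR = (0.486/0.514) / (p/(1 − p)) with p = 0.146 + k/150. k = 0: 5.53; 1: 5.25; 3: 4.75; 5: 4.33; 8: 3.80. DYS power stays at or above 99.9%.
- All on 75 mg, with 48.6% containing the k women: the true rate is 0.486 − k/150. The OR free of them is 5.38 (k = 1), 5.10 (3), 4.84 (5), 4.46 (8), against 5.53 reported. Joint power stays at or above 98.6%.
- Extreme case, no true DYS effect and all k in one active arm: the chance of a false DYS win is about 1.9% (k = 1), 3.9% (3) or 7.2% (5), against 1.25% nominal in that direction. NMPP would still have to be won.

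**5. Pregnancy.** Assumptions not in the documents: 28-day cycle, bleeding on cycle days 1 to 5, test positive from day 28, detection and last dose at a 28-day visit. The last dose then falls on cycle day 28 to 55. The window is bleed-free if (day − 27) > 5, that is days 33 to 55: 23/28 = 82%. Bleeding of 3 to 7 days, a positive test from day 26 to 32, and last dose on or one day before the visit give 64% to 100%.

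**The case against.** The strongest reply is that this is rare, hard to reach and harmless. These drugs are prohibited, the sponsor must be told, and SAP 3.2 can remove the user from the PP Set. Protocol 5.3 itself describes breakthrough bleeding on progestins and reduced flow, not absence of bleeding, on combined oral contraceptives. One spotting day replaces the zero with a computed mean. Each dose must also win NMPP, which the DYS zero rule does not touch and which drives joint power. All of that stands, and it limits the size of the problem. It does not supply a rule: no FAS analysis reclassifies a hormone user who stays on study drug.

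A reader might infer more than the documents support:

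- *Any pregnancy or hormone start counts as DYS response.* It can, under the conditions in step 2, but not automatically. A pregnant woman whose last dose falls on cycle day 28 to 32 still has bleeding days in her window under the step 5 assumptions.
- *The protocol allows hormones alongside study drug.* It is silent; it merely does not require a stop.
- *The effect is diluted because these events cluster on placebo.* No source supports that. Protocol 5.7 reports eleven Phase 2 pregnancies without denominator or arm. An excess on placebo would work against linzagolix, an excess on an active arm in its favour.
- *The PP Set overlooks pregnancy.* A woman withdrawn for pregnancy has not completed six months and is already outside it.

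**Conclusion.** The point holds for prohibited hormonal therapy. The zero rule ignores cause, the estimand has no strategy for such therapy, and the FAS co-primary can therefore credit randomized treatment with a DYS response produced by another hormone. The classification gap follows from the text alone. Its size rests on assumed counts: 0.67 points per woman, and a 75 mg DYS odds ratio of about 4.33 instead of 5.53 if five fall on placebo. Frequency and direction are unknown. Power is essentially unaffected for up to eight such women in one arm, so the harm is to the estimate and its interpretation. Pregnancy follows the same path but is largely covered by SAP 4.6.5.1 and the PP definition. This is a cheap improvement worth making, not a threat to the trial's conclusion.

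**What to change.** In SAP 4.6.2.1.1:

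1. Add an intercurrent event under the composite strategy already used for analgesics: a woman who starts a hormonal endometriosis therapy prohibited by exclusion criterion 7 (the hormonal items, a to f and k) before the end of her Month 3 window is a non-responder.
2. Do not apply the DYS zero rule to a bleed-free window that follows such a start or a conception. Say explicitly that DYS is then not assessable, so that the existing rule for non-assessable women applies (non-response; change from baseline of zero for numeric endpoints).
3. State how the DYS analgesic criterion is judged when the window has no bleeding day. SAP 4.6.5.3 already defines an all-days version that could serve as a model.

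If the data are already unblinded, run this as a labelled FAS sensitivity analysis and leave the primary analysis as specified.

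The cost is a few sentences. Concomitant medication and pregnancy data are already collected (Protocol 10.6 and 12.6). The downside is a few more non-responders. No change to the PP list is needed.
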